10.3 Investigator Documentation

Prior to beginning the study, the investigator will be asked to comply with ICH E6(R2) 8.2 and Title 21 of the CFR by providing the following essential documents, including but not limited to:

- IRB/IEC approval
- Original investigator-signed investigator agreement page of the protocol
- Form FDA 1572, fully executed, and all updates on a new fully executed Form FDA 1572
- Curriculum vitae for the investigator and each subinvestigator listed on Form FDA 1572
- Financial disclosure information to allow the sponsor to submit complete and accurate certification or disclosure statements required under 21 CFR 54. In addition, the investigators must provide to the sponsor a commitment to promptly update this information if any relevant changes occur during the course of the investigation and for 1 year after the completion of the study
- IRB/IEC-approved informed consent, samples of site advertisements for recruitment for this study, and any other written information regarding this study that is to be provided to the patient
- Laboratory certifications and normal ranges for any local laboratories used by the site, in accordance with 42 CFR 493

10.4 Study Conduct

The investigator agrees that the study will be conducted according to the principles of ICH E6(R2). The investigator will conduct all aspects of this study in accordance with all national, state, and local laws or regulations. Study information from this protocol will be posted on publicly available clinical trial registers before enrollment of patients begins.

10.5 Adherence to Protocol

The investigator agrees to conduct the study as outlined in this protocol in accordance with ICH E6(R2) and all applicable guidelines and regulations.

10.6 Adverse Events and Study Report Requirements

By participating in this study, the investigator agrees to submit reports of SAEs to the sponsor and/or IRB/IEC according to the timeline and method outlined in the protocol. In addition, the investigator agrees to submit annual reports to the study site IRB/IEC as appropriate.

10.7 Investigator's Final Report

Upon completion of the study, the investigator, where applicable, should inform the institution; the investigator/institution should provide the IRB/IEC with a summary of the study's outcome and the sponsor and regulatory authorities with any reports required.

10.8 Records Retention

Essential documents should be retained until at least 2 years after the last approval of a marketing application in an ICH region and until there are no pending or contemplated marketing applications in an ICH region or at least 2 years have elapsed since the formal discontinuation of clinical development of the investigational study drug. These documents should be retained for a longer period, however, if required by the applicable regulatory requirements or by an agreement with the sponsor. It is the responsibility of the sponsor to inform the investigator/institution as to when these documents no longer need to be retained.

10.9 Publications

After completion of the study, the data may be considered for reporting at a scientific meeting or for publication in a scientific journal. In these cases, the sponsor will be responsible for these activities and will work with the investigators to determine how the manuscript is written and edited, the number and order of authors, the publication to which it will be submitted, and other related issues. The sponsor has final approval authority over all such issues.

Data are the property of the sponsor and cannot be published without prior authorization from the sponsor, but data and publication thereof will not be unduly withheld.

11 Study Management

The administrative structure will include a scientific steering committee and event adjudication committee.

The scientific steering committee, composed of key opinion leaders who are expert in the treatment of patients with cervical dystonia, will consult with the sponsor on the design of the study protocol, review the data, and analyze the data incorporated into the final study report.

11.1 Monitoring

11.1.1 External Data Monitoring Committee

No data monitoring committee is planned for this study.

11.1.2 Monitoring of the Study

The clinical monitor, as a representative of the sponsor, has the obligation to follow the study closely. [REDACTED]

11.1.3 Inspection of Records

Investigators and institutions involved in the study will permit study-related monitoring, audits, IRB/IEC review, and regulatory inspections by providing direct access to all study records. [REDACTED]

[REDACTED]

[REDACTED] [REDACTED]

[REDACTED]

[REDACTED]

11.2 Management of Protocol Amendments and Deviations

11.2.1 Modification of the Protocol

Any changes in this research activity, except those necessary to remove an apparent, immediate hazard to the patient, must be reviewed and approved by the sponsor or its

designee. Amendments to the protocol must be submitted in writing to the investigator's IRB/IEC for approval before patients can be enrolled into an amended protocol.

11.2.2 Protocol Deviations

The investigator or designee must document and explain in the patient's source documentation any deviation from the approved protocol. [REDACTED]

Term	Percentage
GMOs	85%
Organic	82%
Natural	80%
Artificial	75%
Organic	88%
Natural	86%
Artificial	78%
Organic	90%
Natural	89%
Artificial	77%
Organic	84%
Natural	83%
Artificial	76%
Organic	87%
Natural	85%
Artificial	79%
Organic	86%
Natural	84%
Artificial	78%
Organic	89%
Natural	87%
Artificial	81%
Organic	92%
Natural	90%
Artificial	83%

11.3 Study Termination

Although Aeon Biopharma has every intention of completing the study, Aeon Biopharma reserves the right to discontinue the study at any time for clinical or administrative reasons.

The end of the study is defined as the date on which the last patient completes the EOS visit (20 weeks after initial treatment), patient withdrawal (for any reason), or study discontinuation by the sponsor.

[figure not shown]
11.4 Final Report

Whether the study is completed or prematurely terminated, the sponsor will ensure that the clinical study reports (CSRs) are prepared and provided to the regulatory agencies as required by the applicable regulatory requirements. The sponsor will also ensure that the CSRs in marketing applications meet the standards of the ICH harmonised tripartite guideline E3: Structure and Content of Clinical Study Reports.

Where required by applicable regulatory requirements, an investigator signatory will be identified for the approval of the CSR. The investigator will be provided reasonable access to statistical tables, figures, and relevant reports and will have the opportunity to review the complete study results.

[figure not shown]
Upon completion of the CSR, the sponsor will provide the investigator with the full summary of the study results. The investigator is encouraged to share the summary results with the study patients, as appropriate. The study results will be posted on publicly available clinical trial registers.

[figure not shown]
12 References

[figure not shown]

The list of references is heavily redacted, consisting of approximately 30-40 entries, each represented by a solid black horizontal bar of varying lengths. The redaction is most dense in the upper half of the list, with some shorter bars appearing in the middle and lower sections.

Topic	Percentage
Global warming	98
Evolution	95
Black holes	50
Big Bang theory	40
Quantum mechanics	85
Relativity	88
Neuroscience	75
String theory	72
Dark matter	80
Dark energy	82
Climate change	92
Plate tectonics	90
Big data	93
Artificial intelligence	94
Neuroscience	75
String theory	72
Dark matter	80
Dark energy	82
Climate change	92
Plate tectonics	90
Big data	93
Artificial intelligence	94

[figure not shown]

[figure not shown]

[figure not shown]
[REDACTED]

[figure not shown]
[REDACTED]

[figure not shown]
13.2 TWSTRS Scale

13.3 Dysphagia Severity Scale

As a result, the *labeled* and *unlabeled* data are combined to form a single *supervised* dataset. This dataset is then used to train a machine learning model, which is used to predict the labels for the *unlabeled* data. This process is known as semi-supervised learning.

© 2006 by the author. All rights reserved.

ANSWER

ANSWER

[REDACTED]

For more information, contact the Office of the Vice President for Research and Economic Development at [contact] or [contact].

11. **What is the primary purpose of the following statement?**

For more information, contact the Office of the Vice President for Research and Economic Development at [contact] or [contact].

For more information, contact the Office of the Vice President for Research and Economic Development at [contact] or [contact].

11. **What is the primary purpose of the *Journal of Clinical Endocrinology and Metabolism*?**

© 2013 Pearson Education, Inc. All Rights Reserved. May not be copied, scanned, or duplicated, in whole or in part. Due to electronic rights, some third party content may be suppressed from the eBook and/or eChapter(s). Editorial review has determined that any suppressed content does not materially affect the overall learning experience. Pearson Education, Inc. reserves the right to remove additional content at any time if subsequent rights restrictions require it.

1000

[figure not shown]
Black box

© 2013 Pearson Education, Inc.

[figure not shown]
13.4 CGI-S and CGI-C Scales

13.5 PGI-S Scale

13.6 PGI-C Scale

13.7 C-SSRS Scale

8.3.3. Pulse	23
8.3.4. Saturation	23
8.3.5. Respiratory Rate	23
8.3.6. Weight	23
8.3.7. COLUMBIA-SUICIDE SEVERITY RATING SCALE (C-SSRS)	25
8.8. SENSITIVITY ANALYSES	25
9. EFFICACY ANALYSIS.....	26
9.1. SECONDARY ESTIMANDS	26
9.1.1. TWSTRS	26
9.1.2. CGI-S	28
9.1.3. PGI-S	29
9.1.4. CGI-C	29
9.1.5. PGI-C	30
9.2. SENSITIVITY ANALYSES	30
9.3. DYSPHAGIA SEVERITY SCALE	31
10. INTERIM ANALYSIS	31
11. CHANGES IN THE PLANNED ANALYSIS	31
12. REFERENCES.....	31
14. APPENDICES	34

List of Abbreviations

ADA	anti-drug antibodies
AE	adverse event
ANCOVA	analysis of covariance
C-SSRS	Columbia-Suicide Severity Rating Scale
CD	Cervical dystonia
CGI-C	Clinical Global Impression of Change
CI	confidence interval
CRF	case report form
ECG	electrocardiogram
eICF	electronic informed consent form
EOS	end of study
FAS	Full Analysis Set
FEV1	forced expiratory volume in 1 second
FVC	forced vital capacity
ICF	informed consent form
ICH	International Conference on Harmonisation
IRT	interactive response technology
MedDRA	Medical Dictionary for Regulatory Activities
mFAS	Modified Full Analysis Set
PGI-C	Patient Global Impression of Change
PGI-S	Patient Global Impression of Severity
PPS	Protocol Analysis Set
PT	preferred term
OLE	open label extension
SAE	serious adverse event

SOC	system organ class
TEAE	treatment-emergent adverse events
TWSTRS	Toronto Western Spasmodic Torticollis Rating Scale
WHO	World Health Organization

1. Introduction

Cervical dystonia (spasmodic torticollis) is the most common form of focal dystonia, affecting the neck and shoulder muscles (Defazio 2004, Mittal 2019). Cervical dystonia is characterized by abnormal head and neck posture and involuntary head and neck movements. It is often associated with neck and shoulder pain.

Botulinum toxin A is considered first-line therapy for cervical dystonia, helping to improve pain, posture, and disability (Comella 2011, Simpson 2016, Mittal 2019). ABP-450 (prabotulinumtoxinA) is a toxin produced by *Clostridium botulinum*. It blocks neuromuscular transmission by binding to acceptor sites on motor nerve terminals, entering the nerve terminals, and inhibiting the release of acetylcholine. Blocking the release of acetylcholine plays a role in relaxing muscles by reducing muscle activity.

[REDACTED]

PrabotulinumtoxinA was evaluated in multiple non-clinical safety and toxicological tests to determine the pharmacologic and safety profile of the product in complying with International Council for Harmonisation of Technical Requirements for Pharmaceuticals for Human Use (ICH) guidelines/requirements for biologic products. [REDACTED]

[REDACTED]

[REDACTED]

PrabotulinumtoxinA has also been found to be non-inferior to onabotulinumtoxinA (BOTOX®) for the treatment of moderate to severe glabellar lines in adult patients and for upper limb spasticity in stroke patients (Nam 2015, Rzany 2019). The doses of ABP-450 used in the Phase 3 study for upper limb spasticity were similar to the doses of BOTOX® used (no significant differences were seen between the two groups) (Nam 2015).

This Phase 2, multicenter, randomized, double-blind, active- and placebo-controlled study aims to demonstrate the safety and efficacy of ABP-450 doses (low, medium, and high) compared with placebo in patients with cervical dystonia. The current Phase 2 study will help to determine appropriate doses of ABP-450 in this study population.

Clostridium botulinum toxins have become the standard of care for the treatment of patients with cervical dystonia. In addition to onabotulinumtoxinA, abobotulinumtoxinA, incobotulinumtoxinA, and rimabotulinumtoxinB have been approved for the treatment of patients with cervical dystonia. Even though these toxin products have been approved for the treatment of cervical dystonia and are the standard of care in patients with this condition, they do have significant risks associated with their use in these patients. The labels for all these products carry prominent warnings concerning their side effects, such as dysphagia and even death, if they are not carefully administered and the patient monitored while under treatment. Even so, the benefit for all these products is greater than the risks and that is why these products are the standard of care.

Clinical development of drugs has been impacted by the ongoing COVID-19 pandemic. The current study aims to implement several adjustments or mitigations to allow the study to continue despite pandemic-related disruption. To prioritize patient and site staff safety, several planned office visits have been converted to tele-visits to allow the required data collection to meet the study objectives

2. Objectives

2.1. Primary Objective

- To demonstrate the safety of a single treatment of ABP-450 (low, medium, or high dose) compared with placebo in the treatment of cervical dystonia

2.2. Secondary Objective

- To demonstrate the efficacy of a single treatment of ABP-450 (low, medium, or high dose) at Week 4 compared with placebo in the treatment of cervical dystonia

3. Investigational Plan

3.1. Overall Study Design and Plan

This is a Phase 2, multicenter, randomized, double-blind, placebo-controlled study of ABP-450 purified neurotoxin complex for the treatment of cervical dystonia.

Both previously treated patients and those who have never been exposed to botulinum toxin (naïve patients) will be eligible. Pre-treated patients must be stable responders who are receiving no more than 300 units of botulinum toxin type A or 750 units abobotulinumtoxinA. The last injection for those previously treated should be at least 16 weeks prior to treatment in ABP-19000. Botulinum toxin-naïve patients are defined as those not receiving treatment with a botulinum toxin in the head or neck.

Sixty Patients will be randomly assigned (ratio of 1:1:1:1) into 1 of 4 treatment arms: ABP-450 low dose (150 units), ABP-450 medium dose (250 units), ABP-450 high dose (350 units), or placebo. The investigator will be blinded to the dose level. The doses will be prepared to the same volume using appropriate dilution as per the dose level. The volume injected will be equivalent across the doses and placebo. To ensure balance across the treatment groups, randomization will be stratified by previous treatment with BOTOX® (BOTOX® naïve vs. previously treated with BOTOX® within 4-12 months prior to baseline). The safety and efficacy of the three dose cohorts of ABP-450 or placebo will be evaluated over a maximum of 20 weeks. At the completion of the Phase 2 study, all patients, irrespective of treatment group, will have the option to receive treatment with ABP-450 by rolling over into an open-label extension (OLE) study (ABP-19002).

This study will evaluate the safety and efficacy of ABP-450 or placebo over a maximum of 20 weeks. The primary objective will include evaluation of the safety of a single treatment of ABP-450 (low, medium, or high dose) compared with placebo. The secondary objective will include evaluation of the efficacy of a single treatment of ABP-450 (low, medium, or high dose) compared with placebo at Week 4.

3.2. Study Estimands

3.2.1. Primary Estimand

- Proportion of patients who would develop treatment-related serious adverse events (SAEs) during the first 20 weeks of a single treatment cycle when dosed with:
 - Placebo;
 - Low-dose ABP-450 (150 units);
 - Medium-dose ABP-450 (250 units);
 - High-dose ABP-450 (350 units); or
 - Any ABP-450 dose.

[REDACTED]

[REDACTED]

[REDACTED]

[REDACTED]

[REDACTED]

[REDACTED]

[REDACTED]

3.2.2. Secondary Estimands

- Mean difference in change in Toronto Western Spasmodic Torticollis Rating Scale (TWSTRS) total score from baseline to Week 4 for each of low, medium, and high doses of ABP-450 compared with placebo. This is the hypothetical estimand .
- Mean difference in change in the subscale scores of the TWSTRS (disability, severity, and pain) from baseline to Week 4 for each of low, medium, and high doses of ABP-450 compared with placebo. This is the hypothetical estimand.
- Mean difference in change in scores on the Clinical Global Impression of Severity (CGI-S) and Patient Global Impression of Severity (PGI-S) from baseline to Week 4 for each of low, medium, and high doses of ABP-450 compared with placebo. This is the hypothetical estimand.
- Mean difference in scores on the Clinical Global Impression of Change (CGI-C) and Patient Global Impression of Change (PGI-C) for each of low, medium, and

high doses of ABP-450 compared with placebo at Week 4. This is the hypothetical estimand.

3.3. Treatments

The four treatment groups are ABP-450 low dose (150 units), ABP-450 medium dose (250 units), ABP-450 high dose (350 units), and placebo. Investigational study drug is a *Clostridium botulinum* toxin type A

- Investigational study drug vials contain 100 units of lyophilized ABP-450
- Placebo vials contain sodium chloride for injection, USP, 0.9%, preservative-free

A large rectangular area of the page has been completely blacked out, indicating that the original content has been removed or is not to be disclosed.

3.4. Dose Adjustment/Modifications

Investigational study drug dose modifications are not allowed.

4. General Statistical Considerations

The statistical principles applied in the design and planned analyses of this study are consistent with International Council for Harmonisation (ICH) E9 guidelines (ICH 1998).

A thick black horizontal bar, likely a redacted section of text.

Data summaries will be presented by treatment group unless otherwise specified. All efficacy analyses will be based upon the Full Analysis Set (mFAS, Section [REDACTED]
[REDACTED]), and all safety as well as demographic and baseline characteristic analyses will be based upon the Safety Analysis Set (Section 4.3.5). Additional analyses will be performed on selected populations as specified in the sections below.

4.1. Sample Size

Fifteen patients will be randomly assigned to each of four treatment arms (placebo, ABP-450 low dose, ABP-450 medium dose, and ABP-450 high dose) using a 1:1:1:1 ratio and therefore requiring a total of 60 patients. [REDACTED]
[REDACTED]
[REDACTED]
[REDACTED]
[REDACTED]
[REDACTED]
[REDACTED].

4.2. Randomization, Stratification, and Blinding

Approximately 60 patients will be randomly assigned (ratio of 1:1:1:1) into 1 of 4 treatment arms: ABP-450 low dose (150 units), ABP-450 medium dose (250 units), ABP-450 high dose (350 units), or placebo. [REDACTED]

The investigator will be blinded to the dose level. The volume injected will be equivalent across the doses and placebo. To ensure blinding, an appropriate and protocol-trained person at each site, such as a study nurse or other designee, will reconstitute investigational product vials in a manner blinded to the investigator and patient. [REDACTED]

[REDACTED]

[REDACTED]

[REDACTED]

[REDACTED]

[REDACTED] The designated person will then fill the syringe with the investigational product and give the filled syringe in a blinded fashion to the investigator. Appropriate spatial separation is required to ensure blinding. Blinding for the initial phase will be maintained throughout the study until the final assessment for the final patient has been entered into the database and the database lock has been performed.

If patients are unblinded during the study, they will be summarized in a table and presented in a listing.

4.3. Analysis Sets

4.3.1. Screened Set

The Screened Set will consist of all patients who signed informed consent and attended screening Visit 1.

4.3.2. Full Analysis Set (FAS)

The FAS will consist of all randomized patients who received investigational study drug. All analyses using the FAS will group patients according to randomized treatment.

4.3.3. Modified Full Analysis Set (mFAS)

The mFAS will consist of all patients in the FAS, but will exclude patients who have a

[REDACTED]

[REDACTED] All analyses using the mFAS will group patients according to randomized treatment.

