- To demonstrate the efficacy of a single treatment of ABP-450 (low, medium, or high dose) at Week 4 compared with placebo in the treatment of cervical dystonia

Estimands:

Primary Estimand

- Proportion of patients who would develop treatment-related serious adverse events (SAEs) during the first 20 weeks of a single treatment cycle when dosed with:
 - Placebo;
 - Low-dose ABP-450 (150 units);
 - Medium-dose ABP-450 (250 units);
 - High-dose ABP-450 (350 units); or

- Any ABP-450 dose.

Treatment-related SAEs are counted during a single treatment cycle (up to 20 weeks and prior to administering any further treatment) and irrespective of change in background treatment or low doses that were below the set low-dose amount (ie, below 150 units) or high doses that were above the set high-dose amount (ie, above 350 units).

Secondary Estimands

- Mean difference in change in Toronto Western Spasmodic Torticollis Rating Scale (TWSTRS) total score from baseline to Week 4 for each of low, medium, and high doses of ABP-450 compared with placebo. This is the hypothetical estimand, assuming no change in background treatment or further treatment before Week 4 and administration of treatment with the correct dose amount.
- Mean difference in change in the subscale scores of the TWSTRS (disability, severity, and pain) from baseline to Week 4 for each of low, medium, and high doses of ABP-450 compared with placebo. This is the hypothetical estimand assuming no change in background treatment or further treatment before Week 4 and administration of treatment with the correct dose amount.
- Mean difference in change in scores on the Clinical Global Impression of Severity, Patient Global Impression of Severity, Clinical Global Impression of Change, and Patient Global Impression of Change from baseline to Week 4 for each of low, medium, and high doses of ABP-450 compared with placebo. This is the hypothetical estimand, assuming no change in background treatment or further treatment before Week 4

and administration of treatment with the correct dose amount.

For all estimands, the target population is patients diagnosed with cervical dystonia who have not had previous treatment with botulinum toxin within the last 16 weeks, are receiving stable doses of treatment for focal dystonia (eg, anticholinergics and benzodiazepines), and who meet the inclusion/exclusion criteria.

Study Population:

Inclusion Criteria

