7.3 Analysis Sets

The following analysis sets will be used in the statistical analyses.

Full Analysis Set (FAS): The FAS will consist of all patients who received investigational study drug. All analyses using the FAS will group patients according to randomized treatment.

Modified Full Analysis Set (mFAS): The mFAS will consist of all patients in the FAS, but will exclude data points after patients have a significant change to their “stable” background medication, receive a dose outside of the set dose amounts, or receive further treatment. All analyses using the mFAS will group patients according to randomized treatment.

Per-Protocol Analysis Set (PPS): The PPS will consist of all patients in the FAS who received placebo or ABP-450 (according to the set dose amount), but will exclude all patients who

discontinued the study prior to Week 4 or had significant protocol violations affecting evaluation of the primary endpoint. All analyses using the PPS will group patients according to actual treatment received.

Safety Analysis Set: The Safety Analysis Set will consist of all patients who received any investigational study drug. All analyses using the Safety Analysis Set will group patients according to treatment actually received.

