4.3.4. Per-Protocol Analysis Set (PPS)

The PPS will consist of all patients in the FAS who received placebo or ABP-450 (according to the set dose amount), but will exclude all patients who discontinued the study prior to Week 4 or had major protocol deviations which may affect evaluation of the TWSTRS assessment at Week 4. All analyses using the PPS will group patients according to actual treatment received.

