8.8. Sensitivity Analyses

[REDACTED]

[REDACTED]

[REDACTED]

[REDACTED]

[REDACTED]

[REDACTED]

[REDACTED]

[REDACTED]

[figure not shown]
9. Efficacy Analysis

[figure not shown]
Unless otherwise indicated, all inferential efficacy analyses will include all patients in the mFAS. The PPS will also be applied to analyses and summaries on TWSTRS scores. Missing data imputation will be performed as described in each section. Visit windows for efficacy analyses are described in Appendix 14.2. Efficacy analyses will be tabulated by treatment group. Figures will be produced for measures over time.

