9.1. Secondary Estimands

9.1.1. TWSTRS

Most studies leading to the approval of currently available botulinum neurotoxins have used the TWSTRS scale as the primary efficacy measure (Espay 2018, Fernandez 2013). The standard TWSTRS is a comprehensive scale that comprises three subsets to assess motor severity, pain, and disability (Comella 2016). The motor severity subscale consists of 10 items, with variable scaling and weighting. It also includes a disability subscale with 6 items and a pain scale with 3 items. The total score is the sum of each of the subscales.

Mean difference in change in the subscale scores of TWSTRS (disability, severity, and pain) from baseline to Week 4 for each of low, medium, and high doses of ABP-450 compared to placebo will also be analyzed [REDACTED]

Summary statistics for change from baseline of TWSTRS total score and subscale scores (disability, severity, and pain) every 4 weeks will be tabulated by treatment group and displayed in figures over time. [REDACTED]

Summary statistics for time to loss of $\geq 80\%$ of peak treatment effect for patients dosed on ABP-450 will be tabulated by treatment group. [REDACTED]

[REDACTED]

[REDACTED]

[REDACTED]
[REDACTED]
[REDACTED]
[REDACTED]
[REDACTED]
[REDACTED]
[REDACTED]

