9.1.2. CGI-S

CGI-S enables the clinician to rate the severity of the patient's illness, relative to their past experience with patients who have the same diagnosis, on a 7-point scale ranging from "normal" to "among the most extremely ill patients" (Guy 1976). In this study, a 4-point scale will be used (see Appendix 0).

CGI-S scores will be measured at Baseline Visit 2 (Day 1), Visit 4 (Week 4), Visit 6 (Week 8), Visit 8 (Week 12), Visit 10 (Week 16), and EOS (Week 20). [REDACTED]

[REDACTED]
[REDACTED]
[REDACTED]
[REDACTED]
[REDACTED]
[REDACTED]
[REDACTED]
[REDACTED]
[REDACTED]
[REDACTED]
[REDACTED]
[REDACTED]

[REDACTED] A listing of CGI-S scores will be provided.

[REDACTED]
[REDACTED]
[REDACTED]
[REDACTED]
[REDACTED]
[REDACTED]

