9.2. Sensitivity Analyses

Sensitivity analysis will be performed for mean difference in TWSTRS total score from baseline to Week 4 for each low, medium, and high doses of ABP-450 compared to placebo, [REDACTED]
[REDACTED]

[REDACTED]. Similarly, mean difference in change in the subscale scores of TWSTRS (disability, severity, and pain) from baseline to Week 4 for each low, medium, and high doses of ABP-450 compared with placebo will be made, [REDACTED]

Additional sensitivity analyses will be performed for mean difference in TWSTRS total score (and subscale scores) from baseline to Week 4 for each low, medium, and high doses of ABP-450 compared to placebo for the FAS using the same analysis described in Section 9.1.1.

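### The protocol and the visible SAP text define the mFAS with different units of exclusion: data points after an event versus whole patients

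*SAP*

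**What the plan says.** Both documents start the mFAS from the FAS and then diverge on what is removed.

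- Protocol 7.3: the set keeps all FAS patients "but will exclude data points after patients have a significant change to their" stable background medication, after a dose outside the set amounts, or after further treatment. The unit is the data point.
- SAP 4.3.3: "The mFAS will consist of all patients in the FAS, but will exclude patients who have a". The unit is the patient. The conditions, and any time limit, are redacted.

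Both group mFAS patients by randomised treatment. SAP section 9 states that, unless otherwise indicated, "all inferential efficacy analyses will include all patients in the mFAS". SAP section 4 is less clear: it names the Full Analysis Set for efficacy but puts the mFAS abbreviation beside it.

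The protocol synopsis defines the Week 4 efficacy estimands for TWSTRS, CGI and PGI in these terms: "This is the hypothetical estimand, assuming no change in background treatment or further treatment before Week 4", and assuming the correct dose amount. The SAP also plans results beyond Week 4: "Summary statistics for change from baseline of TWSTRS total score and subscale scores (disability, severity, and pain) every 4 weeks will be tabulated". CGI and PGI are scored at Weeks 4, 8, 12, 16 and 20.

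**The concern.** An analysis set should deliver the data that the estimand asks for. The estimand here is hypothetical and concerns only what happens before Week 4. The protocol's rule fits it: the patient stays, values before the event count, and values after the event are treated as missing. A whole-patient rule can do something else. It can remove a randomised patient from the Week 4 comparison because of an event at, say, Week 14, when the Week 4 value is already in hand and valid. It can also turn a missing value, which the analysis would have to handle, into a patient who is simply absent.

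At stake are the Week 4 dose-versus-placebo comparisons, with 15 patients planned per arm, and the over-time tables and figures. Two programmers, one working from each document, could build different mFAS datasets.

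**Working it through.** **Is the conflict in readable text?** Yes. In both sentences the object of the exclusion stands before any redaction. Hidden words in SAP 4.3.3 can add conditions or a time limit, but the thing excluded remains the patient. Two other places in the SAP fit that reading without proving it. The PPS, plainly a patient-level set, uses the same construction ("exclude all patients who discontinued the study prior to Week 4"). SAP 5.1 counts patients in the FAS and the mFAS separately, although under the protocol's rule the two counts would always be equal.

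**Which values differ?** The visible post-baseline efficacy visits are Weeks 4, 8, 12, 16 and 20, so there are 5. Let an event fall after visit k and before visit k+1. The protocol's rule keeps k values. A patient rule without a limit keeps 0 and so loses k valid values. A patient rule limited to events before Week 4 keeps all 5 when k is at least 1, so 5 − k post-event values stay in unless the hidden text drops them.

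| Event falls | Protocol keeps | Valid values lost, patient rule, no limit | Post-event values kept, patient rule, Week 4 limit |
|---|---|---|---|
| Before Week 4 | 0 | 0 (patient leaves the set) | 0 (patient leaves the set) |
| Weeks 4–8 | 1 | 1 | 4 |
| Weeks 8–12 | 2 | 2 | 3 |
| Weeks 12–16 | 3 | 3 | 2 |
| Weeks 16–20 | 4 | 4 | 1 |

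Without a limit, every event after the Week 4 assessment costs that patient's Week 4 value. A dose outside the set amounts occurs at the single injection, so it always belongs in the first row.

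**The first row is not a guarantee of agreement.** Under the protocol's rule that patient stays in the mFAS with Week 4 missing. SAP section 9 says imputation is described section by section, but the methods are not readable. If Week 4 is imputed, the patient contributes under the protocol's rule and not under the SAP's, even with a Week 4 limit.

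**Precision (illustration).** Assume 0 to 3 patients per arm have an event after Week 4 and there is no limit. The standard error of an arm difference scales as √(15/n): 1.00 at n = 15, 1.04 at 14, 1.07 at 13 and 1.12 at 12. At 15 versus 15 it is √(2/15) = 0.365 SD.

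**Power and shift (illustration).** The documents show no effect size, SD, alpha or event rate. The figures below assume a two-sided 5% t-test without covariates, effects d of 0.4, 0.8 and 1.2 SD, placebo event rates f after Week 4 of 10% to 30%, and no Week 4 limit. They use a correlation rho between poor Week 4 response and the later event. With c = Φ⁻¹(1 − f) and h = φ/Φ, the shift toward the null is rho × [h(c) − h(c + d·rho)].

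| d (SD) | Power, 15 v 15 | Power, 12 v 12 | Shift, rho = 0 | Shift, rho = 0.3 | Shift, rho = 0.5 |
|---|---|---|---|---|---|
| 0.4 | 0.185 | 0.155 | 0 | 0.01–0.02 | 0.03–0.05 |
| 0.8 | 0.562 | 0.466 | 0 | 0.02–0.03 | 0.05–0.09 |
| 1.2 | 0.887 | 0.802 | 0 | 0.03–0.05 | 0.06–0.13 |

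The largest shift, 0.126 SD, is 0.126/0.365 = 0.35 of one standard error. If the later event is unrelated to response, there is no shift.

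**The case against.** The strongest reply is that the SAP sentence stops at a redaction. The hidden text may hold a Week 4 limit and a rule for later values, and SAP section 11 may declare the change. The protocol also says that its statistical section is brief and that the SAP supplies the details and definitions, so a refined set definition is not in itself an error. All of this stands as a limit on the consequence. It does not remove the difference in unit, which is in readable text.

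Several further points also stand. The visible text mentions further treatment with ABP-450 only as an option in the extension study after completion, so events after Week 4 may be few, and nothing readable supports a 10% to 30% rate. For TWSTRS the SAP plans an FAS analysis: "Additional sensitivity analyses will be performed for mean difference in TWSTRS total score (and subscale scores) from baseline to Week 4", with subscales, by the same method. Efficacy is a secondary objective.

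A reader might infer more than the documents allow:

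- **That the SAP changed the protocol without saying so.** Section 11 cannot be read, so this is not shown.
- **That the Week 4 effect is biased or the trial loses a stated amount of power.** This needs the absence of a time limit, an event rate, an effect size and, for bias, a link between response and later events. None of these is visible.
- **The opposite: that a Week 4 limit would make the two rules agree at Week 4.** This does not follow either, because events before Week 4 can be handled differently through imputation.

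**Conclusion.** The point holds as a minor discrepancy. Protocol 7.3 excludes data points after an event, and the visible wording of SAP 4.3.3 excludes patients, in the set that is the default for inferential efficacy analyses. Confidence is high on the conflict of wording and low on its consequence.

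The effect on the Week 4 results is unknown and may be nil. It depends on two things that cannot be read: whether the SAP limits exclusion to events before Week 4, and how missing Week 4 values are handled. The visit counts rest on the visible schedule alone. The standard-error, power and shift figures are illustrations under assumed inputs and should not be quoted as properties of this trial.

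Patients stay grouped as randomised. TWSTRS is partly protected by the FAS analysis, CGI and PGI have no visible equivalent, and the primary safety estimand is not affected.

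**What to change.** Reconcile SAP 4.3.3 with Protocol 7.3 before database lock, when the protocol requires the SAP to be final. The protocol's data-point rule is preferable because it matches the hypothetical estimand and keeps randomised patients in the set. Wording to this effect would do: all FAS patients belong to the mFAS; assessments after a qualifying event are set to missing; a Week 4 value is excluded only for an event before the Week 4 assessment.

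If patient-level exclusion is intended, confirm that SAP section 11 declares it, gives its time limit, and says how post-event values at later visits are treated. If the hidden text already does this, confirmation is enough.

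The cost is one sentence and a record-level flag in the analysis dataset. No new data are needed.
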